2.1 Study rationale and purpose

Histone deacetylase inhibitors (HDACi) are a class of agents regulating the acetylation of core histones responsible for the epigenetic control of tumor suppressor gene expression and other genes responsible for cell differentiation and apoptosis (Schreiber 2002). Acetylated histones remain in a relaxed state allowing for the transcription of genes. HDACi block the action of

histone deacetylases (HDAC) from removing these moieties and repressing transcription. HDACi also promote the acetylation of other non-histone proteins including heat shock protein, HSP90, a chaperone for various proteins offering protection from ubiquitin directed proteasomal degradation (Bali 2005). HDACi promote cell cycle growth arrest and accumulation in G1 or G2-M and apoptosis involving both mitochondrial and receptor ligand-mediated pathways. Previous in vitro studies investigating the use of HDACi in the HEL cell line and JAK2V617F+ cells from PV and ET patients have shown selective reduction in the mutant JAK2 clone with preservation of the wild type cells (Guerini 2007). These studies also make the point that not only are direct targets of the mutated JAK2 pathway such as signal transducers and activators 3 and 5 (STAT3/5) down-modulated, but so are downstream target genes such as PRV-1. JAK2V617F specific attenuation was only seen at the protein level as JAK2 mRNA levels remained unaffected and may reflect either preferential mutant directed proteasomal degradation, selective acetylation of the mutant form or acetylation of other stabilizing proteins. PMF is also characterized by an increased proportion of circulating peripheral blood CD34+ hematopoietic stem cells and ex vivo exposure of PMF CD34+ cells to sequential DNA methyltransferase (DNMT) inhibitor and HDACi has been shown previously to dramatically reduce the burden of malignant progenitor cells as detected by a reduction in JAK2V617F allele burden (Shi 2007).

PANOBINOSTAT is a novel cinnamic hydroxamic HDACi and a very potent pan-HDAC inhibitor specifically enhancing acetylation on H3 and H4 and HSP90 (Glaser 2007). Targeted inhibition of HDAC6, a member of the class IIB HDACs, by PANOBINOSTAT has been shown to enhance acetylation of HSP90 and disrupt its chaperone function leading to the degradation of various client proteins such as BCR/ABL, AKT, c-RAF, and FLT-3(Bali 2005; George 2005). JAK2 is also a client protein of HSP90 and inhibition of this chaperone protein results in the degradation of JAK2 and impairment in cytokine signaling (Shang 2006). The use of PANOBINOSTAT in MF patients would be an additional or alternative mechanism of down-regulating the JAK2V617F mutant clone by direct inhibition of JAK2V617F and suppression of the various downstream targets and effectors responsible for cell growth, differentiation and survival with the ultimate goal of modifying the disease phenotype. PANOBINOSTAT has shown activity in patients with MF as described in the previous section. PANOBINOSTAT will be provided in the oral formulation for ease of administration in the outpatient setting and due to the fact that PK/PD studies have already been completed in previous studies using oral PANOBINOSTAT [CPANOBINOSTATB 2101] and both bioavailability and histone acetylation data as mentioned previously favor oral dosing on a TIW schedule in this patient population.

Due to the encouraging, but limited results of RUXOLITINIB alone in patients with MF, we propose a phase I/II study of PANOBINOSTAT in combination with RUXOLITINIB in patients with MF. A standard 3+3 dose escalation schema with RUXOLITINIB at a starting dose of 10mg PO BID given continuously will be combined with PANOBINOSTAT given QOW on 28 day cycle with continuous RUXOLITINIB at 10mg PO BID. This schedule will allow for determination of both the dose limiting toxicity (DLT) and maximum tolerated dose (MTD) of both drugs as well as evidence of clinical response as defined by the International Working Group (IWG) criteria. Based on our previous work with PANOBINOSTAT (not yet

published), we hypothesize that prolonged administration at low doses is required to effect changes in the peripheral blood and ultimately in the bone marrow that reflect disease modification and potential improvement in outcome.

At this time there still exists no standard medical treatment for myelofibrosis and of the many drugs that have been used in the past (hydroxyurea, melphalan, danazol, interferon-alfa, thalidomide, lenalidomide) and presently being investigated (JAK2-TKI, HDACI, mTORi pomalidomide) have not been shown to affect the natural history and progression of disease. These drugs have individually shown the ability to induce response rates as measured in spleen reduction, amelioration of constitutional symptoms and to some degree modulation of hematologic profile and reduction in JAK2V617F allele burden. We believe that the combination of the RUXOLITINIB and PANOBINOSTAT is a novel and rational approach to the treatment of MF based on both pre-clinical science and clinical data as single agents in MF.

To further the benefit seen with RUXOLITINIB in patients with MF, PANOBINOSTAT will be added to the treatment regimen to act synergistically in the blockade of the dysregulated pathway driving this disease. See Section 2.4 for more information on the preclinical study demonstrating the synergistic activity exerted by the combination of PANOBINOSTAT and the JAK inhibitor TG101209 against CD34⁺ primary MPN cells and JAK2V617F-expressing cell lines. This synergy will hopefully provide enhanced anti-proliferative activity in patients and reduce overall treatment related toxicity by using lower than single agent maximum tolerated dose levels. This clinical trial will be a single arm, safety and dose-finding phase I/II study, with a primary endpoint within the phase II portion of IWG-MRT treatment response and secondary endpoints of spleen volume response and changes in exploratory biomarkers

2.2 Rationale for the study design

This is a Phase I/II single arm, dose escalation study with expansion at the RPTD to assess efficacy and exploratory endpoints and further define safety and toxicity. This dose escalation process will be based on the toxicity profile. Following the determination of the MTD and/or potential RPTD, a dose expansion phase will be conducted at that dose to further define the safety and tolerability of the combination. See Section 10.4.2.1 for further details of the dose expansion cohort. Also during the dose expansion phase, biomarker data will be collected.

2.3 Rationale for dose and regimen selection

Since thrombocytopenia has been established as the DLT of PANOBINOSTAT, a dosing schedule of QOW will first be attempted in the early dose escalation cohorts since data from [CLBH589B2102] suggests QOW dosing decreased the incidence and time to severe treatment related thrombocytopenia as well as the duration of thrombocytopenia. Refer to Table 2-1 for more detailed information.

Table 2-1

Comparison of dose reductions, duration of exposure, relative dose intensity and thrombocytopenia between QW and QOW schedule with oral PANOBINOSTAT in patients with HL in study CLBH589B2102

Parameters Analyzed	Every Week Schedule (QW)				Every Other Week Schedule (QOW)		
	30 mg TIW	40 mg TIW	60 mg TIW	All	45 mg TIW	60 mg TIW	All
	N=2	N=15	N=5	N=22	N=3	N=7	N=10
Dose Reductions (%)							
None	100	40	60	50	100	71	80
1 dose reduction	0	27	40	27	0	29	20
≥2 dose reductions	0	33	0	23	0	0	0
Thrombocytopenia							
Time to grade 3/4 (median, days)	86.5	12	8	12	N/A (>376)	64	N/A (>208)
Duration (median, days)	4.5	8	5	7	N/A	7	7
Maximum duration (days)	6	26	29	29	N/A	8	8
Exposure (median, days)	392.5	115	176	136	348	131	260
Relative dose intensity	91.0 %	62.1%	47.3%	57.3%	92.9%	96.7%	94.5%

Abbreviation: N/A = not applicable (median not reached because Grade 3/4 thrombocytopenia has not yet occurred)

From study [INC424-251], anemia and thrombocytopenia were the most frequently reported grade 3 or 4 events. While thrombocytopenia was the most frequently reported treatment emergent adverse event (TEAE) leading to study drug interruption (18.8%), only 3.2% of the patients required discontinuation of study medication. The only other TEAEs leading to discontinuation that occurred in more than one patient were anemia (2.6%), multi-organ failure (1.3%), and acute myeloid leukemia (1.3%). Analysis of grade 3 and 4 thrombocytopenia by initial treatment group also showed a clear dose response. Patients who began therapy at lower doses (10-15mg BID) were less likely to have grade 3 thrombocytopenia, and no patient receiving these doses had grade 4 thrombocytopenia or worsening anemia (data on file: Novartis). Refer to Section 1.3.3 for more detailed information on these events.

2.4 Rationale for choice of combination drugs

In a preclinical study (Wang 2009), it was demonstrated that compared with either agent alone, combined treatment with PANOBINOSTAT and TG101209 (a JAK2 TK inhibitor) is more effective in attenuating not only p-STAT3 and p-STAT5, but also the mutant JAK2V617F. This effect was more pronounced when PANOBINOSTAT was combined with lower concentrations of TG101209. Preclinically this combination also showed a synergistic increase in cytotoxicity for cells expressing the JAK mutation (Wang 2009). HEL cells treated with PANOBINOSTAT showed an approximately 40% depletion of the mRNA expression of JAK2 (Wang 2009). PANOBINOSTAT has also been shown to induce hyperacetylation and

inhibition of the chaperone function of HSP90, resulting in proteasomal degradation of HSP90 client proteins which includes JAK2. The distinct mechanisms of action of PANOBINOSTAT in addition to the blockade of the JAK/STAT pathway provided by RUXOLITINIB, may allow for greater disease control at lower doses of each of these agents to avoid toxicities. There is no predicted pharmacokinetic interaction between these two drugs, and synergistic toxicities are not anticipated. See Section 1.4.1 and Section 1.4.2 for further details.

From this study, the JAK2V617F mutation allele burden was measured pre- and post-treatment from 10 patients. The median percent of mutant JAK2 pre-treatment was 27%, and the median percent post-treatment was 10% indicating a significant median decline in the JAK2V617F allelic burden (DeAngelo 2010).

From study INC424-251, in the 34 patients for whom data were available the mean maximal suppression of 13% from baseline was seen after 12 cycles of therapy (Verstovsek 2010).

As both of these agents modify the overall JAK2V617F allele burden, given sufficient follow up this may prove to have meaningful clinical benefit.

3 Objectives and endpoints

Objectives:

- Evaluate the tolerability and safety of combination RUXOLITINIB and PANOBINOSTAT in patients with MF in chronic and accelerated phase.
- Assess clinicopathologic response of MF patients treated with RUXOLITINIB and PANOBINOSTAT.
- Assess changes in biomarkers of disease in relation to response to combination treatment with oral PANOBINOSTAT and RUXOLITINIB.
- Explore genetic and epigenetic predictors of disease response to combination therapy in MF.

Endpoints:

- Determine the Dose Limiting Toxicities (DLTs) of each agent in combination.
- Characterize the adverse events (AEs) and serious adverse events (SAEs) of combination therapy.
- Establish the Maximally Tolerated Doses (MTDs) and the Recommended Phase Two Doses (RPTDs) for each agent in combination.
- Assessing clinical response by International Working Group for Myelofibrosis Research and Treatment (IWG-MRT) consensus criteria.
 - Spleen reduction by palpation on exam.
 - Peripheral blood count and morphology normalization.
 - Bone marrow histopathology and fibrosis.
- Evaluate reduction in spleen volume by MRI/CT.
- Evaluation bone marrow response in terms of cellularity, histopathology and fibrosis in patients treated with RUXOLITINIB and PANOBINOSTAT.

- Evaluation of histone H3/H4 acetylation, JAK2V617F mononuclear allele burden, degree of circulating CD34+ hematopoietic cells in the peripheral blood; CXCR4 expression in CD34+ hematopoietic cells; changes in cytokine and other plasma protein levels from baseline.
- Assess if the presence of JAK2V617F, TET2, ASXL1, EZH2 and other MPN markers can predict clinical response to combination therapy

4 Study design

4.1 Description of study design

Phase I/II open label, single institution, study of induction RUXOLITINIB followed by concurrent administration of RUXOLITINIB and PANOBINOSTAT in a 3+3 cohort dose escalation schema in eligible patients with MF (see Figure 4-2). Screening for this study will have a window of 56 days and start on day -84 with signing of informed consent. See Figure 4-1 A and B. Eligible patients will begin induction phase therapy on day -28, receiving single agent RUXOLITINIB PO BID daily for 28 days. The dose of RUXOLITINIB in the induction cycle days -28 to 0 will be the same dose that the patient will receive in the assigned combination cycles. Patients who maintain a platelet count $\geq 50,000/\mu\text{L}$ at Day 1 will then receive concomitant PANOBINOSTAT PO TIW QOW or PO TIW QW depending on the cohort assignment. The induction phase of the Phase I study is not the evaluable phase I component and AEs that are noted in the induction phase will not constitute a dose limiting toxicity (DLT) and patients who do not maintain a platelet count $>50 \times 10^9/\text{L}$ will be removed and will not be able to continue onto the combination drug evaluable phase I period of 28 days and will not be counted in the evaluable phase I cohort for the purposes of dose escalation.

Phase I

The first 28 days of combination therapy will be the evaluable phase I portion of the study. Patients who do not experience a defined DLT in the dose evaluation stage of phase I can remain on study receiving combination drug therapy for a total of 6 cycles (cycles 2-6). See Figure 4-1 A. AEs will continue to be recorded on all patients (phase I and II) receiving combination therapy beyond the first cycle of the study. Dose escalation rules are based on the standard 3+3 design as shown in Figure 4-2.

Note that in this Phase I study, the initial cohort(s) will fix the dose of RUXOLITINIB and escalate the dose of PANOBINOSTAT. Thus, the first endpoint will be to find the MTD of PANOBINOSTAT associated with a fixed dose of 10 mg of RUXOLITINIB. At that point, the dose of PANOBINOSTAT will be fixed at the MTD just mentioned, and RUXOLITINIB will be escalated to 15 mg. The rules of the 3+3 design will govern whether 15 mg is an acceptable dose for RUXOLITINIB in combination with the MTD of PANOBINOSTAT. The rules of the 3+3 design will again be employed to decide on the frequency of administration of PANOBINOSTAT.

Phase I patients who complete a total of 6 cycles of combination therapy will be assessed for clinical response by IWG-MRT criteria. Patients who achieve at least Stable Disease (SD) by IWG-MRT (Table 4-1) can remain on therapy indefinitely or until disease progression or drug toxicity as assessed by the investigators in the Phase I extension stage. After 24 cycles, stable patients may be seen every other month at the discretion of the investigator. At the discretion of the investigator, phase I patients who have completed 6 cycles of therapy with a minimum of SD can also be dose escalated at that time to the RPTD once it is determined. These patients will not be considered for evaluation of response in Phase II.

Myelosuppression is expected and anticipated given the known toxicity profiles of these drugs in single agent therapy for MF. During the dose evaluation stage, Days 1-28, while both drugs are administered in combination, platelet transfusions will not be allowed to avoid the predetermined DLT of platelet count $<10 \times 10^9/L$ or any platelet count with grade 3 bleeding. If a platelet transfusion is indicated by best clinical practice guidelines and the PI feels it is necessary to transfuse a patient in these 28 days of the phase I study even at a platelet count $>10 \times 10^9/L$, then the patient will be transfused and will come off study and this will be considered a DLT. Platelet transfusions are allowed and should be given when clinically indicated and at the discretion of the investigator in Phase I continuation stage and extension stage. This would not necessarily require discontinuation from the study.

Phase II

Expansion stage [Cycles 1-6]

Once a RPTD is determined from the dose escalation phase I part of this trial, the dose expansion of the phase-II part of this trial will commence with 16 additional patients added to the 6 original RPTD cohort from phase I to total 22 patients. See Figure 4-1 B. IWG-MRT response criteria will be applied at the end of cycle 6 and this will include spleen volume measurement by MRI/CT and bone marrow biopsy to appreciate changes in morphology, degree of reticulin/collagen fibrosis, cytogenetics and molecular markers. Patients who have obtained at least SD by IWG-MRT can remain on study receiving combination therapy in the phase II extension stage.

Extension stage [Cycles 7+]

[figure not shown]
In this part of phase II, patients have obtained at least SD by IWG-MRT after 6 cycles of combination therapy and will continue to be treated with dose modifications and stopping rules that are the same as the expansion stage. Patients will continue to be followed for signs of response on each monthly visit. After 24 cycles, stable patients may be seen every other month at the discretion of the investigator. Repeat imaging of the spleen and bone marrow biopsy with repeat cytogenetic and molecular testing when appropriate can be performed at the discretion of the investigator for the purpose of assessment of response or disease progression. Additional biomarker assessments can also be made at intervals determined by the clinical course and at the discretion of the investigator.

Platelet transfusions are allowed in the Phase II portion of this trial and should be given when clinically indicated. Specific instructions are provided for dose modifications and holding of study drugs as outlined in Table 6.2.3. Red blood cell transfusion are allowed and anemia does not require dose holding or modification until after cycle 6 if the PI believes the study

[figure not shown]
drugs are primarily the cause of worsening anemia and in these cases the instructions for dose holding and modification can be followed as outlined in Table 6.2.3.

Figure 4-1 Study Design

A. Phase I Study design

B. Phase II study design

*Phase II expansion stage is Days 1 to 168 (end of cycle 6)

**Phase II extension stage is days 169 and beyond (cycle 7+)

Figure 4-2 Dose escalation rules for 3+3 phase I study design

[figure not shown]

TABLE 4-1 International Working Group (IWG) consensus criteria for treatment response in myelofibrosis with myeloid metaplasia

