Screening for this study will have a window of 56 days and start on day -84 with signing of informed consent. See Figure 4-1 A and B. Eligible patients will begin induction phase therapy on day -28, receiving single agent RUXOLITINIB PO BID daily for 28 days. Patients who maintain a platelet count $\geq 50,000/\mu\text{l}$ at Day 1 will then receive concomitant PANOBINOSTAT PO TIW QOW or PO TIW QW depending on the cohort assignment.

The first 28 days of combination therapy will be the evaluable phase I portion of the study. Patients who do not experience a defined DLT in the evaluable phase I period can remain on study receiving combination drug therapy for a total of 6 cycles (cycles 2-6). See Figure 4-1 A. AEs will continue to be recorded on all patients (phase I and II) receiving combination therapy beyond the first cycle of the study. Dose escalation rules are based on the standard 3+3 design as shown in Figure 4-2.

Phase I patients who complete a total of 6 cycles of combination therapy will be assessed for clinical response by IWG-MRT criteria. Patients who achieve at least Stable Disease (SD) by IWG-MRT (Table 4-2) can remain on therapy indefinitely or until disease progression or drug toxicity as assessed by the investigators. At the discretion of the investigator, phase I patients who have completed 6 cycles of therapy with a minimum of SD can also be dose escalated/deescalated at that time to the RPTD once it is determined. These patients will not be considered for evaluation of response in Phase II.

Once a RPTD is determined from the dose escalation phase I part of this trial, the dose expansion phase-II part of this trial will commence with additional patients added to the original RPTD cohort from phase I to a sample size of 22. See Figure 4-1 B. IWG-MRT response criteria will be applied at the end of cycle 6 and this will include spleen volume

measurement by MRI and bone marrow biopsy to appreciate changes in morphology, degree of reticulin/collagen fibrosis, cytogenetics and molecular markers. Patients who have obtained at least SD by IWG-MRT can remain on study receiving combination therapy in the dose extension stage of Phase II.

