1.4.2 Integrative toxicological assessment of PANOBINOSTAT and RUXOLITINIB in combination

When combining both compounds the potential for overlapping toxicities needs to be considered. For PANOBINOSTAT the predominant toxicities seen preclinically consisted of: myelosuppression, lymphoid depletion, degeneration of the intestinal epithelium, variable effects on the thyroid epithelium and thyroid hormones, anabolic effects on bone (manifested

as hyperstosis), atrophy/degeneration of testes, prostate and ovarian follicles and embryolethality and fetotoxicity (manifested as decreased fetal body weight). For RUXOLITINIB the predominant toxicities seen preclinically consisted of: myelosuppression, lymphoid depletion resulting in decreased erythropoiesis and lymphopoiesis, immunosuppression resulting in secondary infections in dogs, and embryo-lethality and fetotoxicity (manifested as decreased fetal body weight). For both compounds most of the findings were reversible or showed trends toward reversibility and can be readily monitored in the clinical setting. Preliminary clinical data available from ongoing trials in myelofibrosis with PANOBINOSTAT or RUXOLITINIB as single agents indicate thrombocytopenia as the principal overlapping dose-limiting toxicity. Fatigue, neutropenia and diarrhea are also listed as toxicities for PANOBINOSTAT. Although no combination PANOBINOSTAT and RUXOLITINIB toxicity studies have been conducted, based on clinical data with each, it appears likely that thrombocytopenia will be dose limiting when these agents are combined in the clinical setting.

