6.2.9 Dose escalation

Dose escalation post-toxicity after cycle 2 (Day 29)

Patients who have experienced treatment-related \geq grade 3 toxicity of any nature aside from thrombocytopenia, or grade 4 thrombocytopenia may not dose re-escalate nor return to the dose level for which this toxicity was encountered.

At the discretion of the Investigator, a patient may undergo dose re-escalation if it is felt to be in the best interest of the patient, and they have met the criteria as outlined in Section 6.2.6, 6.2.7, or 6.2.8 depending on the toxicity. For patients who undergo dose re-escalation, platelet counts must be obtained at least weekly for 4 weeks, and then at least every second week for the next 4 weeks. Thereafter, they may resume monthly evaluations.

Patients may continue treatment with RUXOLITINIB and PANOBINOSTAT until they experience unacceptable toxicity that precludes any further treatment, disease progression, and/or at the discretion of the Investigator. Patients will be discontinued from the study if they withdraw consent, or if the treating physician judges that further therapy with RUXOLITINIB and PANOBINOSTAT is no longer in the patient's best interest.

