6.2.9.1 Intra-patient dose escalation Post MTD and/or RPTD determination (non-toxicity related)

Intra-patient dose escalation may be permitted by the Investigator following 13 patients treated for at least 2 cycles at the RPTD. During the course of study treatment, patients can be dose-escalated to the next higher dose level only once every two cycles, provided that ALL of the following criteria are met:

- Inadequate efficacy is seen with the current dose level, as defined by the observation of one or both of the following:
 - Not achieving at least a 50% reduction in palpable spleen length compared to baseline
 - Lack of meaningful improvement in disease symptoms based on the Investigator's expert judgment
- No treatment related toxicity has occurred with the current dose level, resulting in treatment reduction or interruption or discontinuation in the previous 56 days
- The higher dose with which the patient is to be treated does not exceed the MTD and/or RPTD
- Platelet counts must be obtained at least weekly for 4 weeks, and then at least every second week for the next 4 weeks after escalation. Thereafter, they may resume monthly evaluations.

There is no limit to the number of times the study drug may be increased for each patient, provided the above rules are followed for each subsequent dose escalation. The same rules for dose reductions as outlined in Section 6.2.7 apply to these patients.

The rules for intra-patient dose escalation described above apply only to those patients who have undergone one and only one dose reduction. Once a patient undergoes a dose reduction due to treatment-related toxicity, the patient may not have a dose increase unless they have been on a stable dose for at least 28 days with no dose interruptions.

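### Section 4.1 lets Phase I patients move up to the RPTD without tying the move to the platelet schedule in 6.2.9.1, and the SAE table in 10.5.1 does not follow dose changes

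*Combined protocol and SAP*

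**What the plan says.** **The move.** Section 4.1 (Phase I) provides that patients who finish 6 cycles with at least stable disease "can also be dose escalated at that time to the RPTD once it is determined", at the investigator's discretion. The Summary has the same permission and adds the downward direction: such patients "can also be dose escalated/deescalated at that time to the RPTD once it is determined". Neither place gives a platelet schedule or refers to 6.2.9 or 6.2.9.1.

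**Platelet monitoring after a dose increase.** Section 6.2.9 concerns increases after toxicity: "For patients who undergo dose re-escalation, platelet counts must be obtained at least weekly for 4 weeks", followed by counts every second week for 4 weeks, and then "Thereafter, they may resume monthly evaluations". Section 6.2.9.1 concerns escalation after the MTD or RPTD is set, for reasons other than toxicity, capped at the MTD or RPTD. It has the same schedule: weekly for 4 weeks, then "at least every second week for the next 4 weeks after escalation". It also sets conditions that 4.1 lacks. These include 13 patients treated for at least 2 cycles at the RPTD before any such escalation, and one dose level per two cycles. Its final paragraph states: "The rules for intra-patient dose escalation described above apply only to those patients who have undergone one and only one dose reduction".

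**Safety tables.** Section 10.5.1 tabulates SAEs by initial dose level, and then calls for AE and SAE analysis that includes dose level and cycle. Sections 10.5.2.1 and 10.5.2.2 refer to dose level without the word initial. None of these sections says whether dose level means the dose assigned or the dose at onset. Section 10.3 lists daily dose by patient.

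**The concern.** Section 1.4.2 expects the main toxicity to be platelet-related: "it appears likely that thrombocytopenia will be dose limiting when these agents are combined in the clinical setting". Table 6.2.3 interrupts treatment below 20 x 10^9/L, but that rule acts only when a count is taken. Section 7.2.5 requires hematology results to be reviewed before drug is given, leaves more frequent testing to discretion, and patients dose themselves at home between visits.

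The move can be large. By Table 6-2, going from cohort 1 to the cohort 4b dose doubles panobinostat from 60 to 120 mg per cycle and raises ruxolitinib from 10 to 15 mg BID. The cohort 7 dose is 240 mg of panobinostat per cycle. A patient who tolerated a low dose without any reduction is a natural candidate for the move, and is also the patient whom the scope sentence in 6.2.9.1 leaves out.

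The reporting issue is separate. In a table by initial dose level, events after a move up are counted against a lower dose, and events after a reduction against a higher one. It therefore affects every dose change, not only these moves.

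**Working it through.** **1. Does either platelet rule reach a never-reduced Phase I patient who moves up?**

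- 6.2.9: its schedule is attached to re-escalation after toxicity. A patient never reduced is not re-escalating, so the schedule does not apply.
- 6.2.9.1: title, dose ceiling and schedule all fit. The final paragraph requires exactly one dose reduction; this patient has had none. Read literally, the section does not apply.
- If 6.2.9.1 is nevertheless meant to govern, its 13-patient gate and one-level-per-two-cycles limit conflict with the direct move in 4.1. Under either reading the text needs repair.

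**2. Platelet counts in the 8 weeks after a move.**

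- Required by 6.2.9 and 6.2.9.1: 4 weekly + 2 every second week = 6.
- Without that schedule, counts follow the visits. The Phase I grid in Appendix 2 is unreadable in this copy, so visit spacing is an assumption:
  - every 2 weeks: 8/2 = 4 counts, gap 6 - 4 = 2
  - monthly: 8/4 = 2 counts, gap 6 - 2 = 4
  - every other month (allowed after 24 cycles): 8/8 = 1 count, gap 6 - 1 = 5
- Monthly is the best-supported case, because 6.2.9 and 6.2.9.1 both speak of resuming monthly evaluations.

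**3. How many patients could move up?**

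The plan's own figures in 10.8 reproduce: Phase I maximum 12 + 5 x 6 = 42; trial maximum 42 + 16 = 58; minimum 12 + 2 + 3 + 16 = 33.

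Not all of these patients can move. In 10.4.2.1 a cohort that is not the last grows from 3 to 6 only after a DLT among the first 3. Section 6.2.7 removes a patient with a DLT in Days 1-28. An expanded cohort of 6 therefore supplies at most 6 - 1 = 5 movers.

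- Cohorts 1-3: 12 enrolled. The minimum-size calculation adds 3 patients to bring cohort 3 to 6, so cohort 3 had 3, and cohorts 1 and 2 together had 12 - 3 = 9. One of those two was thus expanded, with at least one DLT. Maximum movers: 12 - 1 = 11.
- RPTD at 4a: 11.
- RPTD at 4b: 11 + 5 (from 4a) = 16.
- RPTD at cohort 7: 11 + 4 x 5 (from 4a, 4b, 5, 6) = 31.

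**4. Share of patients ever treated at the RPTD who are absent from its row in the initial-dose table.** Formula: m/(22 + m), with m movers.

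| Movers | Share | Extra counts at 4 per mover |
|---|---|---|
| 0 | 0/22 = 0% | 0 |
| 11 | 11/33 = 33% | 44 |
| 16 | 16/38 = 42% | 64 |
| 31 | 31/53 = 58% | 124 |

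Each non-zero row is a ceiling: every eligible patient would have to reach 6 cycles with at least stable disease and be moved.

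**The case against.** The strongest reply is that the protocol already contains the schedule. A reader might infer from 4.1 alone that no platelet monitoring is prescribed after these moves. The documents do not support that: 6.2.9.1 is titled for escalation after the RPTD is set, is capped at the RPTD, and gives the counts. Its scope sentence also sits badly with its own heading, which excludes toxicity-related changes, and may be a drafting slip. This stands as far as intent goes. It does not remove the literal exclusion, nor the conflict over the gate and the step size.

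A reader might also infer that SAE reporting as a whole assigns later events to the starting dose. That is true of one table only. Section 10.5.1 also asks for dose level and cycle, 10.5.2.2 uses dose level, and the patient listings allow dose at onset to be reconstructed. What remains is that no table is defined by dose at onset.

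A reader might subtract the 6 RPTD patients from 42 and expect up to 36 movers. The 3+3 rules with removal of DLT patients bring this to about 31, unless cohorts are expanded at discretion under 6.2.4.

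Finally, the bar in 6.2.9, under which patients with the specified toxicities "may not dose re-escalate nor return to the dose level for which this toxicity was encountered", is not limited by the route of escalation, so 4.1 need not repeat it.

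**Conclusion.** The point holds as a minor safety-monitoring and reporting correction. Read literally, the plan leaves a never-reduced Phase I patient who moves up to the RPTD without the platelet schedule that it prescribes for comparable increases. The shortfall is about 4 counts in 8 weeks if extension visits are monthly, and 2 to 5 over the spacings considered. The number of such patients is unknown and may be 0. The ceilings of about 11, 16 and 31 rest on at least one removed DLT patient per expanded cohort and on no discretionary expansion.

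In the initial-dose SAE table, up to 33%, 42% or 58% of patients ever treated at the RPTD would be missing from its row, according to whether the RPTD is at 4a, 4b or cohort 7.

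A reader might infer that dose selection or the efficacy result is compromised. Neither is: the move is possible only after the RPTD has been determined, and 4.1 excludes these patients from the Phase II response evaluation.

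**What to change.** 1. In 4.1 and the Summary, state that any increase to the RPTD follows the 6.2.9.1 platelet schedule, whether or not the patient has had a dose reduction. Correct the scope sentence in 6.2.9.1 to match. State whether its 13-patient gate and its limit of one level per two cycles apply to these moves.
2. In 10.5.1 and 10.5.2.2, add AE and SAE tables by the dose level of each drug at onset, using the last level taken if the drug is on hold. One patient can then appear in several rows, so use patients or patient-cycles exposed at each level as the denominator. Keep the initial-dose table as a second view.

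The cost is amendment wording in the Summary, 4.1, 6.2.9.1, 10.5.1 and 10.5.2.2, and one further set of tables from dose data that 10.3 already lists. With monthly visits it adds about 4 platelet counts per mover, from 0 to about 124 in total. No additional patients are needed.
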